9.6.3 Summaries of Baseline Characteristics, Demographics, and Other Analyses

The comparability of the treatment groups for each relevant demographic and baseline characteristic will be assessed by the use of tables and/or graphs. No statistical hypothesis tests will be performed on these characteristics. The number and percentage of participants screened and randomized and the primary reasons for screening failure and discontinuation will be displayed. Demographic variables, baseline characteristics, primary and secondary diagnoses, and prior and concomitant therapies will be summarized by treatment either by descriptive statistics or categorical tables.

9.7 Interim Analyses

Periodic review of data to include safety and study conduct will be performed by an external Data Monitoring Committee (DMC). An internal unblinded statistician and unblinded programmer who otherwise have no other responsibilities associated with the study or the ertugliflozin program will support the DMC.

Additionally, one PK IA will be performed to estimate ertugliflozin exposure in pediatric T2DM participants. The PK IA will be conducted when ~30 participants on study medication have completed **Visit 4/Week 6** (with the expectation that ~20 of those participants would be on ertugliflozin). An unblinded PK analyst, external to the Sponsor, will perform the PK IA and present the results to the DMC. The unblinded PK analyst will have no other responsibilities associated with the study or the ertugliflozin program.

The DMC will serve as the primary reviewer of the results of the PK IA and will make recommendations regarding the continuation of the second randomization to the Executive Oversight Committee (EOC). The PK IA will compare the median dose-normalized trough concentration to a 2.0 ng/mL/mg cutoff. This cutoff was determined by simulations based on

adult PK data with details provided in Appendix 12. If the median dose-normalized trough concentration at the time of the IA is >2.0 ng/mL/mg, the DMC may recommend the 15 mg dose be down-titrated to 5 mg, and the second randomization discontinued. If the median trough concentration is ≤ 2.0 ng/mL/mg, then the study will continue with the second randomization, and up-titrate to ertugliflozin 15 mg if they meet eligibility criteria. With a sample of ~ 20 ertugliflozin participants, the PK IA is expected to result in a decision to down-titrate the 15 mg dose and discontinue the second randomization 90.9% of the time if the mean pediatric clearance is $\le 60\%$ of the adult clearance.

If the second randomization is discontinued, ongoing participants who have up-titrated to ertugliflozin 15 mg/day will have an Unscheduled Visit as soon as possible to be down-titrated to ertugliflozin 5 mg/day in a blinded manner, participants in the placebo group who have been mock up-titrated will also be mock down-titrated. If the 15 mg arm is dropped then hypotheses H2 and H3 will not be tested.

Study enrollment will be ongoing at the time of the PK IA. Blinding to treatment assignment will be maintained at all investigational sites. Results of the PK IA will not be shared with the investigators prior to the completion of the study. Study monitors will remain blinded. The EOC may be unblinded to results at the treatment level in order to act on these recommendations. The extent to which individuals are unblinded with respect to results of the PK IA will be documented by the internal unblinded statistician, who will be different from the unblinded PK analyst.

Additional details such as DMC meeting frequency and conduct, governance, and communication with the EOC will be provided in the DMC Charter.

9.8 Multiplicity

The type 1 error rate for the Bayesian methodology addressing the primary hypothesis under the TP estimand was estimated via simulation to be 0.10. If the success criterion for the primary hypothesis (H1) is met under the TP estimand, then hypotheses H2 will be tested at alpha = 0.05. If H2 is successful then H3 will be tested at alpha = 0.05. The overall study wise type 1 error rate will be greater than 0.05.

If the 15 mg arm is dropped then hypotheses H2 and H3 will not be tested.

9.9 Sample Size and Power Calculations

This study will randomize approximately 165 participants using a 2:1 randomization ratio at Visit 3/Day 1/Randomization for ertugliflozin and placebo resulting in approximately 110 participants in the ertugliflozin group (combined doses) and 55 participants in the placebo group.

TP Estimand Power

The type 1 error and power (percent of 95% posterior credible intervals <0) were simulated (10,000 simulations) using the rjags and coda packages in R and the credible intervals were

computed using the HDInterval package. With an informative prior, the type 1 error will exceed 0.05. Using the adult data from 8835-007 and a weight parameter of 0.134, a sample size of 165 will provide approximately 80% power to detect a true difference of -0.6% in the mean change from baseline in A1C between ertugliflozin and placebo, given the SD=1.5% and discontinuations from study medication as of the primary timepoint are approximately 3.9%. The type 1 error and power were estimated based on the WI approach instead of the RD approach given all randomized participants have either completed on or off study medication or have discontinued from the study in Phase A.

Regarding the secondary hypotheses, the assumptions for the efficacy of the dose-optimized ertugliflozin regimen and of the 5 mg ertugliflozin dose are the same as for the pooled ertugliflozin doses. However, the power for the secondary hypotheses will be lower than that of the primary hypothesis on account of the weighting scheme. Based on simulations, the percent reduction in power is 13% of the primary hypothesis power. Thus, the estimated power for each secondary hypothesis is 70%.

TE Estimand Power

Assuming 86% of the participants will have data at Week 24 (14% with missing data due to discontinuation from study medication or censoring after initiation of rescue), 95 participants in the combined ertugliflozin arm and 47 in the placebo arm will provide at least 80% power for the primary hypothesis test assuming that the between-group difference in A1C change from baseline at Week 24 is -0.75% and using a SD of 1.5%. Assumptions of cumulative attrition rates and covariance matrix at Week 6, Week 12 and Week 24 are listed below:

- 1. The cumulative attrition rates (due to dropout and/or censoring due to discontinuation of study medication or initiation of rescue) at Week 6, Week 12, and Week 24 are 4%, 8% and 14%.
- 2. The conditional covariance matrix is

1.11	0.8	0.6
0.8	1.17	0.8
0.6	0.8	2.25

9.10 Subgroup Analyses

To determine whether the treatment effect is consistent across various subgroups, the between-group treatment effect for the primary variable will be summarized and plotted within each category of each subgroup. Treatment groups will be consistent with the primary analysis: ertugliflozin (combined doses) and placebo. Subgroups analyses will be performed only for the primary analysis and treatment comparison. The following subgroups will be analyzed:

• Baseline A1C by categories: ≥ or <median A1C

PRODUCT: MK-8835

PROTOCOL/AMENDMENT NO.: 059-04

- Sex (Male, Female)
- Race (White, Black, Asian, American Indian or Alaska Native)
 Participants who report belonging to more than one racial group will each be assigned to the racial group that has the highest risk for Type 2 diabetes in the order of American Indian or Alaska Native, Asian, Black, White [Copeland, K. C., et al 2011].
- Ethnicity (Hispanic or Latino, Not Hispanic or Latino)
- Age at Screening (10 to 14 years of age, 15 to 17 years of age)
- Insulin use at Screening (No, Yes)
- Geographic region (EU, North America, Other)

Under the TP estimand, summary statistics will be provided for each subgroup analysis to include sample sizes, means, medians, standard deviations, and 95% confidence intervals on the differences in means based on a normal distribution.

Under the TE estimand, the subgroup analyses will be based on a repeated measures ANCOVA model including terms for treatment, insulin use, the subgroup, time as a categorical factor, baseline A1C, and the treatment-by-subgroup interaction. Treatment effects and nominal 95% CIs by category for the classification variables listed above will be reported. Formal statistical testing of treatment-by-subgroup interactions will not be performed. Forest plots will be produced for each estimand, which provide the point estimates and 95% CIs for the estimated treatment effect across the categories of subgroups listed above.

Results from the subgroup analyses should be reviewed cautiously. Because sample sizes within subgroups will be smaller than the overall study sample size, estimation may not be precise, and 95% CIs will usually be wide in the subgroup analyses.

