For all efficacy analyses with the exception of exploratory analyses for participants who uptitrated from ertugliflozin 5 mg/day to 15 mg/day, participants will be classified as belonging to the ertugliflozin or placebo group according to their randomized treatment assignment at

Visit 3/Day 1/Randomization regardless of the treatment received during the course of the study.

Any participant randomized at the first or second randomization within the incorrect stratum will be classified according to the intended stratum in all analyses that include stratum. The intended stratum will be derived based on the participant's age and insulin use at Screening Visit/Visit 1 or insulin use at Visit 5/Week 12 as captured in the study database. An accounting of any incorrectly stratified participants will be provided in the CSR.

Week 24

For the primary analysis using the TP estimand, treatment group comparisons for the A1C mean change from baseline at Week 24 will be done using a Bayesian borrowing approach. The Bayesian borrowing approach will be done using an ANCOVA model with treatment, the age and insulin use strata as fixed effects, and the baseline A1C measurement as a covariate with normal priors on the model parameters and a mixture prior distribution on the treatment model effect, δ_p :

$$Y_{\text{Week24}} \sim N(\beta_0 + \beta_1 * \text{Age} + \beta_2 * \text{Insulin Use} + \beta_3 * \text{Baseline A1C} + \delta_p * \text{Treatment}, \sigma^2).$$

The model parameters for intercept, age, insulin use and baseline A1C will have wide normal prior distributions as follows:

$$\beta_i \sim N(0, 100^2), i = 0,1,2,3$$

The treatment effect parameter will have a mixture normal prior with 2 components: an informative prior mean and variance based on the full ITT population from the 8835-007 study and a general skeptical prior. The prior distribution of δ_p is as follows:

$$\delta_p | z = 0 \sim N_{general} (0, (1.5*1.5^2))$$

$$\delta_p | z = 1 \sim N_{adult} (-0.598, 0.066^2)$$

where the weight z has a prior Bernoulli distribution with a parameter, p.

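### Section 9.10 leaves TP subgroup effects unadjusted for baseline A1C and strata, which costs some precision and makes the TP and TE forest plots differ in adjustment as well as estimand

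*Combined protocol and SAP*

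**What the plan says.** For TP subgroups, Section 9.10 states: "Under the TP estimand, summary statistics will be provided for each subgroup analysis to include sample sizes, means, medians, standard deviations", followed by "95% confidence intervals on the differences in means based on a normal distribution". It names no model, baseline covariate or stratum term, and does not say whether the imputed Week 24 values are used.

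For TE subgroups, the same section specifies a "repeated measures ANCOVA model including terms for treatment, insulin use, the subgroup, time as a categorical factor, baseline A1C, and the treatment-by-subgroup interaction".

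The overall TP effect in Section 9.6.1 comes from a Bayesian "ANCOVA model with treatment, the age and insulin use strata as fixed effects, and the baseline A1C measurement as a covariate".

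The TP subgroup results go beyond a table of means: "Forest plots will be produced for each estimand, which provide the point estimates and 95% CIs for the estimated treatment effect". The section advises caution and says "95% CIs will usually be wide in the subgroup analyses", but the reason it gives is the smaller sample size. Formal interaction tests are ruled out.

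**The concern.** Change from baseline in A1C generally depends on baseline A1C. A raw difference in mean change therefore carries variation that a baseline covariate would remove. The plan uses that covariate in the overall TP analysis and in the TE subgroup model, but not in the TP subgroups. Section 6.3.2 stratifies the first randomization by age and insulin use only, so baseline A1C is left to chance within every subgroup.

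Two things are at stake. The TP intervals may be wider than the data require. And a reader who compares the TP and TE forest plots cannot tell whether a difference reflects the estimand or the adjustment. This matters most in regions where TP is primary, because there the unadjusted plot accompanies the primary result.

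**Working it through.** **1. The plan's own figure.** Section 9.9 gives TE power of at least 80% for 95 versus 47 participants, difference 0.75, SD 1.5. SE = 1.5 × √(1/95 + 1/47) = 0.2675, and 0.75/0.2675 = 2.804. Power = Φ(2.804 − 1.96) = 80.06%, assuming two-sided alpha 0.05, which the plan does not state for this test. The figure reproduces (79.5% with the noncentral t). The plan gives no precision figure for subgroups.

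**2. Inputs.**
- Residual SD 1.5: Section 9.9 gives SD 1.5% for both estimands. Its covariance matrix, labelled conditional, has 2.25 = 1.5² at Week 24. I read this as conditional on baseline.
- Allocation 2:1, 165 participants (Section 9.9).
- Baseline SD s and slope b of Week 24 on baseline A1C: not in the documents. Assumed s = 0.8 to 1.0 and b = 0.3 to 0.8.

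**3. Loss of precision.** Raw change has variance 2.25 + (1 − b)²s². After adjustment it is 2.25. The SE ratio, adjusted to raw, is √[2.25 / (2.25 + (1 − b)²s²)]:

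| b | s | variance of raw change | SE ratio | adjusted SE smaller by |
|---|---|---|---|---|
| 0.3 | 1.0 | 2.74 | 0.906 | 9% |
| 0.5 | 1.0 | 2.50 | 0.949 | 5% |
| 0.7 | 1.0 | 2.34 | 0.981 | 2% |
| 0.8 | 0.8 | 2.276 | 0.994 | 1% |

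At b = 1 the ratio is 1 and nothing is lost.

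**4. Interval half-widths** at b = 0.5, s = 1.0. Half-width = 1.96 × SD × √(4.5/N), with SD 1.5 adjusted and √2.50 = 1.581 raw:
- N = 82: 0.69 adjusted, 0.73 raw
- N = 50: 0.88 adjusted, 0.93 raw
- N = 24: 1.27 adjusted, 1.34 raw

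**5. Chance baseline imbalance.** In a subgroup of 40 (27 versus 13), √(1/27 + 1/13) = 0.338. At b = 0.5, s = 1.0, imbalance moves the raw difference with SD 0.5 × 1.0 × 0.338 = 0.17. The residual SE is 1.5 × 0.338 = 0.51. Together, √(0.51² + 0.17²) = 0.53, which is the raw SE. The 0.17 is therefore the same component that produces the 5% in step 3. It is about 10% of the raw variance (0.17²/0.53²).

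**6. Which adjusted analysis helps.** I simulated 1,500 trials per setting: 165 participants, effect −0.6, residual SD 1.5, b = 0.5, s = 1.0, and an assumed insulin prevalence of 40% with a 0.2 effect. Mean full 95% CI widths:

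| Subgroup N | raw, t limits | ANCOVA inside the subgroup | pooled ANCOVA with interaction |
|---|---|---|---|
| 82 | 1.48 | 1.43 | 1.40 |
| 50 | 1.92 | 1.88 | 1.81 |
| 24 | 2.90 | 2.99 | 2.66 |
| 15 | 3.77 | 4.17 | 3.34 |

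A separate run with the same SD, slope and baseline SD gave 2.16, 2.14 and 2.02 at N = 40, and 4.07 inside the subgroup against 3.64 raw at N = 15. At b = 0.8, s = 1.0, the pooled gain is small: 1.42 to 1.41 at N = 82 and 1.85 to 1.81 at N = 50.

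At N = 15, raw intervals with z limits have width 3.42 but cover about 93%. Most of the pooled model's gain there (3.77 − 3.42 = 0.35 of 3.77 − 3.34 = 0.43) thus reflects the critical value, through the shared residual variance, rather than covariate adjustment.

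**The case against.** The strongest reply is that nothing here is invalid. Under randomization the raw difference is unbiased within each subgroup, and with t limits its simulated coverage is close to 95%. The analyses are descriptive, have no interaction test and carry an explicit caution. Stratification limits imbalance on two of the three omitted covariates. The gain depends on a slope and a baseline SD that the documents do not give, and at the favourable end of the slope range it is about 1%. Fitting the primary model's covariates separately in each subgroup would also cost degrees of freedom: it gains almost nothing at N = 40 and loses at N = 24 and below.

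All of this stands, and it limits both the importance of the point and the choice of remedy. It does not explain why one section adjusts the TE subgroups for baseline A1C and leaves the TP subgroups raw, when both feed a forest plot of estimated treatment effects.

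A reader might also infer that the TP plot would show unadjusted subgroup effects beside an adjusted overall effect. Section 9.10 does not say that an overall estimate appears on the plot. The overall TP result is moreover a posterior that borrows from adult data, so a frequentist subgroup ANCOVA would not match it exactly either.

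**Conclusion.** The point holds as a modest matter of precision and consistency. TP subgroup effects are estimated without covariates that the plan already uses for the overall TP effect and, apart from the age stratum, for the TE subgroups. With residual SD 1.5, baseline SD 0.8 to 1.0 and slope 0.3 to 0.8, adjustment would reduce the SE by about 1% to 9%, centrally 5%, and by next to nothing as the slope nears 1. No hypothesis, multiplicity step or primary conclusion depends on it.

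Two stronger readings are not supported. One is that chance baseline imbalance biases the TP subgroup estimates or must produce spurious subgroup differences. Leaving out the covariate leaves imbalance uncorrected but does not create it, and the resulting shift is already part of the raw interval (step 5). The other is that the plan breaks its own promise where it says "Treatment groups will be consistent with the primary analysis". That sentence concerns combined ertugliflozin doses versus placebo, not covariates.

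**What to change.** Replace the TP sentence in Section 9.10 with one ANCOVA of Week 24 A1C per subgroup factor, on all FAS participants. Include treatment, subgroup, treatment-by-subgroup interaction, baseline A1C, age stratum and insulin stratum, dropping a stratum term where it is itself the subgroup factor. Fit it to the same RD- or WI-imputed data as the primary TP analysis and combine by Rubin's rule, stating this explicitly because Section 9.10 is silent on missing data. Plot the adjusted differences with t-based 95% CIs, and keep raw means, medians and SDs as descriptive columns. Do not fit separate ANCOVAs inside small subgroups.

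The cost is a few lines of text and some programming, since every covariate is already in the primary model. The opening of Section 9 lets changes to non-confirmatory analyses go into the supplemental SAP if made before unblinding. The small downside is that the pooled model assumes a common residual variance and common covariate slopes across subgroups. That should be stated with the results.

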9.1 Statistical Analysis Plan Summary

Key elements of the statistical analysis plan are summarized below; the comprehensive plan is provided in Sections 9.2 to 9.12.

Statistical Analysis Plan Summary

Study Design Overview	Ertugliflozin T2DM Pediatric Study		
Treatment Assignment	Participants will be randomized in a 2:1 ratio to the ertugliflozin 5 mg group or placebo group. Randomization will be stratified by age (10 to 14 years of age, 15 to 17 years of age) and insulin use (No, Yes). A second randomization at Visit 5/Week 12 will randomize eligible participants (Section 6.1) in the ertugliflozin 5 mg group in a 1:1 ratio to continue on ertugliflozin 5 mg or up-titrate to ertugliflozin 15 mg. The second randomization will be stratified by insulin use (No, Yes). An IA to assess PK may result in dropping the 15 mg dose group. If this occurs, the second randomization will be discontinued and the participants in the 15 mg group will be down-titrated to the 5 mg dose for the remainder of the study.		
Analysis Populations	Efficacy: Full Analysis Set (FAS) Safety: All Participants as Treated (APaT)		
Primary Endpoint	A1C: Change from baseline at Week 24		
Secondary Endpoints	A1C: Change from baseline at Week 54 FPG: Change from baseline at Week 24 and at Week 54		

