The RD analysis may not be feasible due to insufficient observed Week 24 data post discontinuation of study medication. If the number of RD participants per group is at least 50% of participants who discontinue from study medication per arm, then RD will be the primary approach to impute missing data for the TP estimand. If at least one group has either less than 50% RD participants or fewer than 5 total RD participants, then RD will not be performed, and WI will become the primary analysis method. If the minimum data requirement for the RD method is met, then WI will be implemented as a sensitivity approach for the TP estimand. The WI analysis assumes participants who prematurely discontinued from the study or who have an intermittent missing Week 24 value would have a 'washout' of any potential effect of the assigned study medication.

For all analyses involving simulated data, a seed of 8835059 will be used for random number generation.

A constrained longitudinal data analysis (cLDA) model, based on Liang and Zeger [Liang, K.-Y. and Zeger, S. L. 2000], will be used for analyses addressing the TE estimand for A1C mean change from baseline and FPG mean change from baseline. Time will be treated as a categorical variable so that no restriction is imposed on the trajectory of the means over time. The cLDA model will also adjust for treatment, the age stratum, the insulin use stratum, and the interaction of time by treatment. The cLDA model assumes a common mean across treatment groups at baseline within each age and insulin use category (due to randomization) but different means between categories, and a different mean for each treatment at each of the post-baseline timepoints. In the cLDA model, the response vector consists of baseline and the values observed at each post-baseline timepoint. The treatment difference in terms of mean change from baseline to a given timepoint will be estimated and tested from this model. An unstructured covariance matrix will be used to model the correlation among repeated measurements.

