For H3 - The effect of being randomized to ertugliflozin 5 mg versus placebo.

Specific weighting schemes will be used to test H2 and H3. The weighting schemes are defined as follows:

- All participants on placebo have a weight of 1
- All participants on ertugliflozin who were not re-randomized at Visit 5/Week 12 have a weight of 1
- For H2 the hypothesis comparing dose-optimized ertugliflozin to placebo (weighting scheme A):
 - All participants on ertugliflozin who were re-randomized to 5 mg at Visit 5/Week 12 have a weight of 0
 - All participants on ertugliflozin who were re-randomized to 15 mg at Visit 5/Week 12 have a weight of 2
- For H3 the hypothesis comparing ertugliflozin 5 mg with placebo (weighting scheme B):
 - o Participants who were re-randomized to 5 mg at Visit 5/Week 12 have a weight of 2
 - Participants who were re-randomized to 15 mg at Visit 5/Week 12 have a weight of 0

For the key secondary endpoints, treatment group comparisons for the A1C mean change from baseline at Week 24 will be done using an ANCOVA model with treatment, the age and insulin use strata as fixed effects, and baseline measurement as a covariate. Hypotheses H2 and H3 analyses for RD and WI are shown below.

The RD imputation and analysis steps are as follows for H2 and H3 using Rubin's rule for 100 total imputed datasets:

- 1. Within each imputation sample, do the following:
 - a. Impute missing Week 24 values using a normal distribution where the expected change from baseline value is set to the estimated mean change from baseline value from the RD participants in the same treatment group. The standard deviation will be the RMSE derived from the ANCOVA model described above and estimated based on all participants with Week 24 data.
 - b. After step a, each of the 100 resulting datasets will contain the original non-missing data and the imputed data for those with missing Week 24 values.
- 2. The 100 datasets will be analyzed using a weighted ANCOVA model with Baseline A1C and the two stratification factors as covariates. The weights will be defined as listed above and included in the model using the weight option from SAS PROC MIXED. The 100 weighted ANCOVA-based estimates of the treatment difference will be combined using PROC MIANALYZE based on Rubin's rule, which accounts for between and within imputation variability.

The WI imputation and analysis steps are as follows for H2 and H3:

For participants in the ertugliflozin group:

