- 1) Fit a regression model as $Y_{24} = \beta_0 + \beta_1 * Y_0 + \gamma * X + \text{error}$, where Y_0 and Y_{24} are the placebo group A1C values at Baseline and Week 24, respectively, and X is a matrix for the age and insulin stratum fixed covariates.
- 2) Impute missing Week 24 A1C values for ertugliflozin using the estimated mean from the above model and standard deviation equal to the RMSE from the model.

For participants in the placebo group:

- 1) Fit models according to the intermittent missing data pattern with A1C values from the placebo group only:
 - a. For participants with only Baseline data: $Y_{24} = \beta_0 + \beta_1 * Y_0 + \gamma * X + \text{error}$
 - b. For participants with only Baseline and Week 6 data: $Y_{24} = \beta_0 + \beta_1 * Y_0 + \beta_2 * Y_6 + \gamma * X + \text{error}$
 - c. For participants with only Baseline, Week 6 and Week 12 data: $Y_{24} = \beta_0 + \beta_1 * Y_0 + \beta_2 * Y_6 + \beta_2 * Y_{12} + \gamma * X + error$
- 2) Impute missing Week 24 A1C values for placebo using one of the 3 models above based on the missing data pattern with a mean equal to the mean from the regression model and a standard deviation equal to the RMSE from the model.

Descriptive statistics will be used to summarize the A1C mean change from baseline at Week 24 for the individual ertugliflozin dose arms in the subset of participants who were rerandomized at Visit 5/Week 12. All other continuous efficacy endpoints with the exception

of the 2 key secondary endpoints associated with hypotheses H2 and H3, including the Week 12 A1C change from baseline, will be analyzed following the same cLDA method used for the A1C TE estimand under H1 (combined ertugliflozin doses vs. placebo) and will not be analyzed under the TP estimand.

Week 54

The Week 54 analyses will be based on the same FAS population used for the Week 24 analyses. The statistical models for the analyses at Week 54 will be analogous to those at Week 24, except that no between-group comparisons will be provided for **Week 54**. The efficacy endpoints will be summarized for within-group mean change from baseline with estimates and 95% CIs calculated from the analysis model.

Table 7 summarizes the analysis strategy for primary and secondary efficacy endpoints at Week 24 and at Week 54.

Table 7 Analysis Strategy for Efficacy Variables at Week 24 and at Week 54

Variable	Estimand/Approach	Statistical Method	Missing Data Approach
Primary			

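### The TE subgroup model in Section 9.10 leaves out the age stratum, although randomization was stratified by it and the other fitted Week 24 A1C models include it (minor; free improvement)

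*Combined protocol and SAP*

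**What the plan says.** The Section 9.1 summary states: "Randomization will be stratified by age (10 to 14 years of age, 15 to 17 years of age) and insulin use (No, Yes"). Section 6.3.2 names the same two factors for the first randomization.

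The fitted Week 24 A1C models in Section 9.6.1 carry both factors:

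- Primary TP analysis (Bayesian borrowing): "ANCOVA model with treatment, the age and insulin use strata as fixed effects, and the baseline A1C measurement as a covariate".
- Overall TE analysis: "The cLDA model will also adjust for treatment, the age stratum, the insulin use stratum, and the interaction of time by treatment".
- H2 and H3: "ANCOVA model with treatment, the age and insulin use strata as fixed effects, and baseline measurement as a covariate".
- Washout imputation regressions: "X is a matrix for the age and insulin stratum fixed covariates".

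Section 9.10 gives the TE subgroup model as a repeated measures ANCOVA "including terms for treatment, insulin use, the subgroup, time as a categorical factor, baseline A1C, and the treatment-by-subgroup interaction". Age enters only when it is the subgroup under study, listed as "Age at Screening (10 to 14 years of age, 15 to 17 years of age"), the same cut as the stratum. The TP subgroup analysis in that section fits no model; it reports summary statistics and "95% confidence intervals on the differences in means based on a normal distribution".

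**The concern.** Keeping one stratification factor and dropping the other, without comment, looks like an oversight. Section 9.10 exists to judge whether the effect is consistent across categories. Stratified randomization balances age between arms in the whole trial and, if the strata are crossed, approximately within each insulin category. It does not balance age within categories of sex, race, ethnicity, region or baseline A1C. If A1C change differs by age, an age imbalance in a small category moves that category's estimate in the trial actually run. Age variation that the model does not explain also widens the interval. What is at stake is the readability of a descriptive display, not a confirmatory claim.

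**Working it through.** **Which subgroups are affected.** Section 9.10 lists seven: baseline A1C, sex, race, ethnicity, age, insulin use and region. Age is in the model for its own subgroup, so six remain. For insulin use, age is approximately balanced by design if the strata are crossed, so mainly precision is at issue.

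**Inputs from the documents.** TE planning difference -0.75 and SD 1.5 (variance 2.25); 95 and 47 evaluable participants; 2:1 allocation; n = 165; the Week 6/12/24 covariance matrix (all Section 9.9); at least 30% aged 10 to 14 (Section 4.1).

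**Assumptions.** Age effect b on A1C change of 0.25 to 0.6, with 1.0 as an extreme; share p aged 10 to 14 of 30 to 50%; 2.25 taken as the Week 24 variance with age accounted for; two-sided alpha 0.05 for the power check.

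**The plan's own figure.** 0.86 × 110 = 94.6 and 0.86 × 55 = 47.3, matching 95 and 47. A two-sample comparison with difference 0.75 and SD 1.5 gives power 0.8006, so the stated figure of at least 80% reproduces.

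**Precision.** Omitting age multiplies the standard error by √[(2.25 + b²p(1−p)) / 2.25].

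| b | p = 0.3 | p = 0.5 |
|---|---|---|
| 0.25 | +0.3% | +0.3% |
| 0.5 | +1.2% | +1.4% |
| 0.6 | +1.7% | +2.0% |
| 1.0 | +4.6% | +5.4% |

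For example, at b = 0.6 and p = 0.5: 0.36 × 0.25 = 0.09, and √(2.34/2.25) = 1.020.

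**Bias.** The check used 4,000 simulated trials per setting: n = 165, no attrition, 2:1 in blocks within age by insulin, 40% aged 10 to 14, a half-sample subgroup, and the documents' covariance matrix. With a true Week 24 effect of -0.75, the mean estimate and its SD from a Week 24 model were:

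- b = 0.25: -0.758 (0.347) without age, -0.759 (0.347) with age.
- b = 0.5: -0.753 (0.356) without age, -0.754 (0.353) with age.

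The means agree to 0.001, so there is no systematic bias, and the SDs barely differ.

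**Chance imbalance in one realised trial.** The shift is the age-mix imbalance times b. For an assumed 20-point imbalance, 0.20 × 0.3 = 0.06 and 0.20 × 0.6 = 0.12. Against the TE planning effect, 0.06/0.75 = 8% and 0.12/0.75 = 16%. Simulating an imbalance of at least 20 points between arms, with age balanced overall and the subgroup independent of age, gives:

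| Subgroup size | Probability |
|---|---|
| about 82 (half) | 1–2% |
| about 54 | 7–10% |
| about 41 | 15–18% |
| about 25 | 30–34% |

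The 20-point case is therefore rare for sex or median baseline A1C, and plausible for a small race or region category. The documents do not give category sizes.

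**Comparison with the time-by-treatment terms.** The Section 9.10 list has no time-by-treatment interaction, whereas the overall TE model has one. With a single treatment effect across visits, generalised least squares weights from the Section 9.9 covariance are about 0.51, 0.34 and 0.16 for Weeks 6, 12 and 24. Under an assumed profile of -0.4, -0.6, -0.75 the model targets about -0.52. Profiles of -0.3, -0.5, -0.75 and -0.5, -0.7, -0.75 give about -0.44 and -0.61. Only a flat profile returns -0.75. Adding age changes none of this.

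**The case against.** The strongest reply is that little turns on this. Section 9.10 makes the analyses descriptive: nominal intervals, no formal interaction test, and an explicit caution about imprecision. Its TP subgroup analysis adjusts for nothing, so the covariate set could be called the statistician's choice. Although imbalance grows as a category shrinks, so does the standard error. With an even age split, age noise is 0.3 × 0.5/1.5 = 10% to 0.6 × 0.5/1.5 = 20% of the standard error at any subgroup size, and the unadjusted interval already reflects it. All of this stands and fixes the severity as minor. It does not explain why one stratification factor was kept and the other dropped.

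A reader might go further and infer that dropping age biases the subgroup effects, or that it is why they are not comparable with the overall TE effect. The documents do not support either. Under randomization the expected imbalance is about zero, and in the simulation adding age left the mean estimate unchanged to 0.001. The two TE models differ more through the missing time-by-treatment terms and through treating baseline as a covariate instead of part of the response. Nor can one say that the forest plot sets these estimates beside an age-adjusted overall effect: Section 9.10 describes estimates across the subgroup categories and mentions no overall estimate.

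**Conclusion.** The point holds as a minor inconsistency that costs almost nothing to remove. The TE subgroup model omits a stratification factor that the other fitted Week 24 A1C models include. The consequence is a standard error about 0.3 to 2% larger for age effects of 0.25 to 0.6 (about 5% at 1.0), plus uncorrected chance imbalance in small categories. The 0.06 to 0.12 shift describes one adverse draw, not an expected error. It rests on assumed age effects and an assumed 20-point imbalance, because the documents state no age effect. Nothing confirmatory depends on it.

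**What to change.** In Section 9.10, add the age stratum (10 to 14, 15 to 17) to the terms of the TE subgroup model, and say that it is entered once where age is the subgroup. If the omission was intended, state the reason. The cost is a few words, before unblinding, and one degree of freedom; age is already collected for stratification. The same edit is a convenient place to settle the time-by-treatment terms, which need their own correction before the model yields a Week 24 subgroup effect comparable with the overall one.
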